7.4.5 Follow-up for toxicities

Patients whose treatment is interrupted or permanently discontinued due to an adverse event or abnormal laboratory value must be followed until resolution or stabilization of the event, whichever comes first.

If a patient requires a dose delay of > 28 days from the intended day of the next scheduled dose, then the patient must be discontinued from the study. If however the patient was clearly benefiting from panobinostat therapy, the patient may be able to continue treatment with a dose reduction at the Investigator discretion, after resolution of the adverse event. All patients will be followed for adverse events and serious adverse events for at least 4 weeks following the last dose of oral panobinostat.

7.5 Other concomitant medications

Patients must be instructed not to take any additional medications (including over-the-counter products) during the trial without prior consultation with the investigator. All medications taken within 30 days of enrollment should be recorded. If concomitant therapy must be added or changed within 30 days of enrollment, the reason and name of the drug/therapy should be recorded. Other concomitant medications are collected once at enrollment (within 30 days of screening).

In general, the use of any concomitant medication/therapies deemed necessary for the care of the patient are allowed, including drugs given prophylactically (e.g. antiemetics) with the following exceptions:

- Any medications listed in [Appendix 17.1.1](#) which may cause QTc prolongation or inducing torsades de pointes should not be used.

- Any medications that have the potential to alter serum electrolytes (e.g., diuretics) should be monitored very closely for electrolyte abnormalities as these can contribute to the risk of QT prolongation and ventricular arrhythmias.
- No other investigational therapy should be given to patients
- No anticancer agents other than the study medications administered as part of this study protocol should be given to patients. If such agents are required for a patient then the patient must first be withdrawn from the study.
- Leukocyte growth factors (e.g. G-CSF and GM-CSF) are not to be administered systematically but may be prescribed by the investigator for severe neutropenia if this is thought to be appropriate.
- Medications known to be substrates of the isoenzyme CYP2D6 should be used with caution with panobinostat as panobinostat can inhibit isoenzyme CYP2D6 at low micromolar ranges. Please refer to [Appendices 17.1.2 and 17.1.3](#) for the lists of CYP2D6 substrates.
- Concomitant use of CYP3A4 inhibitors with panobinostat should be used with caution due to a potential increase in panobinostat exposure during concomitant treatment with these drugs.
- Oral contraceptives are generally metabolized by CYP3A4. Since the induction potential of panobinostat to induce CYP3A4 is unknown, patients who are using oral contraceptives as a method of contraception, and are sexually active, should use another effective contraceptive method.

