7.4.3 Dose modifications for prolonged QTc

All cardiac events should be treated as per the local standard of care and referred to a cardiologist if clinically indicated. The localized readings of ECGs will use the Fridericia correction for QTc interval assessment: QTcF. Any final decisions concerning dose modifications or permanently discontinuing the patient from study drug due to QTcF prolongation will be based on the Investigator's clinical assessment. Any plan to deviate from these guidelines must be previously discussed and agreed upon with Novartis.

Patients must have QTcF < 470 msec to be eligible for the trial. If QTcF is \geq 470 msec or above 60 msec from baseline on a screening or pre-dose ECG, correct any electrolyte abnormalities (hypokalemia, hypomagnesemia, hypocalcemia), and conduct triplicate ECGs (5 minutes apart) and calculate average QTcF. If the average QTcF from the triplicate ECGs remains \geq 470 ms, patient must not be dosed. Pre-dose ECG monitoring is mandatory on days 1 and 5 of cycle 1, and day 1 of cycles 2 through 4. Post dose ECG (3 hours (\pm 15 minutes) post dosing) is mandatory only on days 1 and 5 of cycle 1.

If a screening, pre-dose, or post-dose ECG shows a QTcF \geq 500 ms, patient is not eligible for further treatment. If any of these mandatory ECGs show QTcF \geq 470 msec or 60 msec above baseline, dosing should be held and the above specified measures including follow-up triplicate ECGs and correction of electrolyte abnormalities should be performed. If QTcF abnormality resolves, patients should resume treatment and have QTcF checked pre-dose on day 1 of each cycle for at least the next 3 subsequent cycles. Additional QTcF monitoring should be performed if clinically indicated. If a patient cannot be dosed due to prolonged QTcF for more than 7 days since last dose, patient must be discontinued from study treatment.

Table 7-3 Dose Reductions for QTc Prolongation

Time Point	Average QTcF*	Action
Screening and pre-dose cycle 1 day 1	\geq 470 msec	Delay treatment Correct any electrolyte abnormal values ** and repeat ECG, if the average QTcF \geq 470 msec, do not dose
	Above 500 msec	Patient is not eligible

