Pre-dose cycle 1 day 5 Pre-dose day 1 of subsequent cycles	\geq 470 msec or above 60 msec from baseline for any pre-dose ECG after the patient has commenced treatment***	Omit dose If unresolved within 7 days, discontinue treatment If resolved within 7 days, resume treatment at prior dose for initial occurrence or at reduced dose if recurrent
	Above 500 msec	Permanently discontinue treatment
*QTcF: Heart rate corrected QT interval using the Fredericia formula: $QTc = QT/RR^{0.33}$ **: serum potassium, magnesium, calcium, ***If a single pre-dose QTcF is \geq 470 msec or 60 msec from baseline, subsequent ECGs should be performed in triplicate		

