7.4.4 Study drug discontinuation

It will be documented whether or not each patient completed the clinical study. If for any patient either study treatment or observations were discontinued, the reason will be recorded.

Reasons that a patient may discontinue treatment are considered to constitute one of the following:

1. Disease progression
2. Adverse event(s) related to the study drug
3. Abnormal laboratory value(s) related to the study drug
4. Abnormal test procedure result(s) related to the study drug
5. Protocol violation
6. Subject withdrew consent
7. Lost to follow-up
8. Administrative problems
9. New cancer therapy
10. Death

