8.3.6 ECG

A screening 12-lead ECG will be performed to assess study eligibility. Additional 12-lead ECGs will be performed at a minimum at scheduled time points as indicated in Table 8-2. Pre-dose ECG monitoring is required for the first four cycles of treatment. Post-dose ECGs will be required during cycle one, on days 1 and 5. Additional ECG monitoring should be done at the discretion of the Investigator, as clinically indicated. All ECGs will be read locally.

Table 8-2 Cardiac assessment monitoring schedule

Cycle	Day of cycle	ECG monitoring ^a
	Screening ^b	Single ECG to assess eligibility
Cycle 1	1, 5	Pre-dose: Single 12 lead ECG
	1, 5	3 hours (± 15 minutes) post dose: Single 12 lead ECG
Cycle 2 and beyond	1	Pre-dose: Single 12 lead ECG
^a Refer to Table 7-3 for the recommended dose modifications due to QTc interval prolongation ^b The screening ECGs will be analyzed locally to assess eligibility of the patient. (Note: the mean QTc interval at baseline must be ≤ 470 msec for the patient to be eligible for participation in the trial) Note: If no significant QTcF prolongation is noted during the first 4 cycles, the QTc monitoring is no longer required and may be performed at the Investigator’s discretion, if medically indicated.		

All cardiac events should be treated as per the local standard of care and referred to a specialist if clinically indicated. The localized readings of ECGs will use the Fridericia correction with MUSE system: QTcF. Any final decisions concerning dose modifications or permanently discontinuing the patient from study drug due to QTcF prolongation will be based on the assessment performed by the Investigators using QTcF correction derived from MUSE system. Any plan to deviate from these guidelines should be previously discussed and

agreed upon with Novartis. If a patient cannot be dosed due to prolonged QTcF for more than 7 days since last dose, patient should be discontinued from study.

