13.1 Statistical methods and data analysis

This is an open label study of 2 different panobinostat maintenance dosing schedules after autologous HCT in patients with multiple myeloma. There are 2 cohorts and patients will be enrolled sequentially to cohort A, then to cohort B. The sample size is 30 patients for this trial (15 for each cohort). We expect that at least 2/3 of each cohort will complete 12 cycles of maintenance panobinostat (regardless of dose modification) and will be evaluable for the primary endpoint. The widths of 95% confidence interval (CI) are 0.356, 0.438, 0.487, 0.514, and 0.522 when the proportions of patients tolerating 12 cycles of maintenance are 0.9, 0.8, 0.7, 0.6, and 0.5, respectively.

A patient who withdraws from the study due to reasons other than death, disease progression or toxicity will be replaced and is considered as non-evaluable for primary endpoint. The proportion of patients tolerating the therapy will be reported with 95% CI. All 30 patients are eligible for secondary endpoints. We will compute the overall response rates before the transplant, after autologous HCT, and after the completion of maintenance therapy, and at best response. The OS and PFS will be estimated using the Kaplan-Meier method. We will also report the incidences of all grades and grade ≥ 3 toxicities. The two-sided 95% CIs for

proportion, and OS and PFS will be computed using the Clopper-Pearson method and the Greenwood formula, respectively. In addition, the frequency of B cell precursor as well as other cell subsets, and their 95% CI will be evaluated using t-distribution. If data do not meet normality assumption, the power transformation (e.g., log-transformation) will be conducted. Those patients who are not in CR before the transplant would be most suitable for T-effector activity analysis. This will be examined by the paired t-test or the Wilcoxon signed-rank test, depending on the data distribution.

Relative dose intensity (RDI) represents the ratio of the amount of a drug actually delivered [actual dose intensity (DI)] to the amount planned (planned DI). The purpose of calculating RDI is to evaluate whether the planned DI of a chemotherapy treatment was actually achieved which may suggest the feasibility of planned treatment regimen. There are multitude of reports demonstrating a correlation between RDI and survival in cancer treatment.

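### Sections 7.4.5, 7.5 and 8.3.6 take patients off the study rather than off treatment, and nothing keeps them in survival follow-up, so 2-year OS may be censored at next-line therapy

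*Combined protocol and SAP*

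**What the plan says.** Four places in the protocol govern what happens to a patient who stops, and they do not use the same word.

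- **Another anticancer agent.** Section 7.5: "If such agents are required for a patient then the patient must first be withdrawn from the study". Section 7.4.4, under the lead-in "Reasons that a patient may discontinue treatment are considered to constitute one of the following", lists both disease progression and new cancer therapy. It also names stopping treatment and stopping observations as two separate things.
- **Prolonged QTcF, no dosing for more than 7 days.** Section 7.4.3: "patient must be discontinued from study treatment". Table 7-3 agrees: "If unresolved within 7 days, discontinue treatment". Section 8.3.6, for the same trigger: "7 days since last dose, patient should be discontinued from study".
- **Dose delay over 28 days.** Section 7.4.5: "then the patient must be discontinued from the study". Its next sentence lets a patient who is benefiting carry on with treatment at the investigator's discretion.

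On analysis, 2-year PFS and OS are secondary objectives (4.2, 13.1.4). Section 13.1 estimates them by Kaplan-Meier and states: "All 30 patients are eligible for secondary endpoints". It gives no OS censoring rule and no time origin. After treatment, the only general follow-up required is for adverse events, for at least 4 weeks (7.4.5). Table 8-1 ends with a visit 4 weeks (± 14 days) after the first dose of cycle 12.

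**The concern.** Kaplan-Meier treats a censored patient as having the same future risk as those still under observation. In myeloma, a patient who needs another anticancer agent has usually relapsed and is at higher risk of death than one who has not. If a site follows 7.5 to the letter, that patient leaves the study before the new agent starts. Nothing elsewhere obliges anyone to record a later death. The patient would then count as alive up to next-line therapy and drop out of the risk set, and the estimated 2-year OS would move towards the probability of not dying without relapse.

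For PFS the exposure is narrower: a patient withdrawn for a new agent or for toxicity before progression would be censored at that point.

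The QTcF and dose-delay wording raises the same follow-up question for a different group. Those patients leave because of toxicity, not relapse, and the documents do not show which way their loss would push OS.

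**Working it through.** The plan states no OS figure to reproduce. Its only design figures are the confidence-interval widths for completing 12 cycles. They reproduce exactly as Clopper-Pearson widths at n = 15 and have no bearing on OS. The calculation below therefore illustrates direction and order of size only.

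**Model.** Three states with constant monthly hazards: progression λ, death without progression h0, and death after progression h1. Let a = λ + h0.

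- True OS: S(t) = exp(−a·t) + λ·[exp(−h1·t) − exp(−a·t)] / (a − h1).
- Kaplan-Meier limit if every relapse is censored: exp(−h0·t).
- Kaplan-Meier limit if only relapses up to month c are censored and all others are followed: exp(−h0·c)·S(t − c).

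**Inputs from the protocol (section 1.1.1).** Control-arm medians are 23 months (PFS, one lenalidomide maintenance trial) and 27 months (time to progression, the other), with 3-year OS of 80%. Lenalidomide-arm medians are 41 and 46 months, with 3-year OS of 88%. λ = ln 2 / median, and h1 is solved so that S(36) equals the 3-year OS.

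**Assumed.** h0 = 0.0005 to 0.002 per month. No document gives this figure.

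**Length of treatment.** Cycle 12 starts at week 44 and the last visit is 4 weeks later, at week 48, or week 50 with the window. That is 11.0 to 11.5 months, so c = 11.

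**One case in full** (median 27, 3-year OS 80%, h0 = 0.0005):

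- λ = 0.6931/27 = 0.02567, a = 0.02617, solved h1 = 0.0191.
- True S(24) = 0.534 + 0.02567 × (0.632 − 0.534)/(0.02617 − 0.0191) ≈ 0.892.
- All relapses censored: exp(−0.012) = 0.988, a bias of 9.6 points.
- Only relapses to month 11 censored: exp(−0.0055) × S(13) = 0.9945 × 0.960 = 0.955, a bias of 6.3 points.

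**Ranges over the inputs** (SE = √[S(1 − S)/30]):

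| Inputs | True 2-year OS | Bias, relapses to month 24 | Bias, relapses to month 11 |
|---|---|---|---|
| Control arms | 88.4–89.2% | 6.9–9.7 points (1.2–1.7 SE) | 4.6–6.3 points (0.8–1.1 SE) |
| Lenalidomide arms | 92.8–93.7% | 2.5–5.1 points (0.5–1.2 SE) | 1.7–3.5 points (0.4–0.8 SE) |

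**Limits.**

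- The 23- and 41-month figures are PFS, which already counts deaths. They are paired with 3-year OS from the other trial. This matters little: with h0 = 0.0005, medians of 23 and 27 months both give a bias of about 9.6 to 9.7 points.
- The post-relapse death rate matters more. If it is not tied to the protocol's 3-year OS but assumed freely (median survival after progression 12 to 60 months, death without progression 0.5 to 3% a year), the bias with every relapse censored runs from about 3 to 25 points.
- The bias is zero if relapse does not raise the death hazard, and zero if deaths after withdrawal are recorded.

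**The case against.** A reader might infer that the protocol in effect censors OS at relapse and so overstates it. The documents do not support that as a statement of fact. No section says that withdrawal ends collection of vital status or censors OS, and 13.1 counts all 30 patients as eligible for the secondary endpoints. The word study is plainly used loosely: 7.4.5 takes a patient off the study and then allows treatment to go on, and 7.4.4 files progression and new therapy under stopping the drug. The trigger in 7.5 is need for another agent, not relapse itself. As a concomitant-medication rule it most naturally applies during the at most 48 weeks of treatment, so the month-24 column is an upper case.

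Two further inferences fail. The QTcF wording does not lead to censoring at relapse; it is a separate toxicity exit. A 2-year OS also cannot be set against the 3-year rates of 80 to 88% in the introduction. The model's uncensored 2-year OS on control figures (88 to 89%) already reaches the top of that range because the horizon is shorter, and the protocol plans no such comparison.

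All of this stands, and it reduces the claim to a conditional one. It does not remove it. Being eligible for an analysis is not the same as having later deaths collected, and no sentence in the document overrides the instruction in 7.5. It is also fair to say that new wording alone would leave no scheduled contact at 2 years for anyone, so the fix has to cover collection as well.

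**Conclusion.** The passages conflict on whether these events end treatment or end the study, and the plan does not say what happens to survival follow-up afterwards. That much rests on the text alone.

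The consequence is conditional. If sites follow 7.5 literally and later deaths are not collected, OS is censored at next-line therapy and 2-year OS is probably too high. The illustration gives about 2 to 6 points if only relapses during treatment are affected and about 3 to 10 points if every relapse to month 24 is. That is roughly 0.4 to 1.7 standard errors at n = 30. These figures rest on constant hazards, an assumed rate of death without relapse, and background figures from other trials. The direction of bias from the QTcF and dose-delay exits is unknown.

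OS is a secondary, estimation-only endpoint, and the primary completion endpoint is not affected. The point should be fixed because the fix is cheap, but it does not undermine the trial's main aim.

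**What to change.** 1. Reconcile the follow-up wording in 7.4.5, 7.5 and 8.3.6 with 7.4.3 and 7.4.4, so that these events are described as ending study treatment and not survival follow-up. This changes no clinical stopping rule, and no view is taken here on any of them.
2. State that only withdrawal of consent or loss to follow-up ends follow-up.
3. State that progression and vital status are collected to 2 years after treatment stops, for every patient.
4. In 13.1, state that OS is not censored at new therapy, and give the time origin.
5. Optionally, say how PFS treats a switch to another agent without progression.

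The cost is wording in three sections, a few sentences on follow-up and analysis, and some extra status collection, since Table 8-1 schedules no contact after about week 50. With 30 patients that is a small burden.

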7.5.1 Anti-coagulant therapy

Panobinostat therapy is commonly associated with mild to moderate degree of thrombocytopenia. This may lead to an increase in the risk of bleeding with concomitant sodium warfarin (Coumadin®). It is recommended that patients who require anticoagulation therapy while on panobinostat therapy use low molecular weight heparin (LMWH). However, if the use of LMWH is not feasible, patients on sodium warfarin may continue such therapy while on panobinostat but for such patients, a close and frequent monitoring of the coagulation parameters, including PT/INR should be followed and they should be maintained within a therapeutic range. The dose of sodium warfarin may be adjusted as needed while on panobinostat. For patients requiring anti-platelet therapy while on panobinostat, aspirin \leq 325 mg or clopidogrel \leq 75mg daily are allowed while on study. It is recommended that anti-platelet therapy be held if platelet counts fall below $50 \times 10^9/L$.

7.5.2 CYP2D6 Substrates

In *in vitro* assays, panobinostat was shown to inhibit the cytochrome P450 isoenzyme CYP2D6 at low micromolar ranges, thereby suggesting a potential risk of drug-drug interactions with concomitant medications that are also metabolized by CYP2D6. A clinical drug-drug interaction study with dextromethorphan (a CYP2D6 probe drug) and panobinostat is currently ongoing in cancer patients. In the meantime, medications that are known to be CYP2D6 substrates should be used with caution when given concomitantly with panobinostat. Patients must be carefully monitored for signs of toxicity as a result of concomitant

medication which may require dose titration or reduction of the CYP2D6 substrate as medically necessary. Please see Appendices 17.1.2 and 17.1.3, and refer to the following website: <http://medicine.iupui.edu/flockhart/table.htm> for a list of substrates of CYP2D6.

7.5.3 Drugs that can inhibit/induce CYP3A4/5

7.5.3.1 Drugs that can inhibit CYP3A4/5

Panobinostat is metabolized in vitro by CYP3A4/5. A clinical drug-drug interaction study with ketoconazole and panobinostat has recently been completed. The less than 2-fold increase in panobinostat AUC upon co-administration with ketoconazole suggests that CYP3A contribution to the total clearance of panobinostat is low. The observed interaction is not considered clinically relevant, as panobinostat doses at least 2-fold greater than 20 mg (40 and 60 mg) have been safely administered in patients. CYP3A4 inhibitors should have no major impact on the exposure of panobinostat and may be co-administered when medically necessary.

7.5.3.2 Drugs that are potent CYP3A4/5 inducers

As it is with other medications that are metabolized by CYP3A4, clinical judgment is to be exercised when potent CYP3A4 inducers are concomitantly taken with panobinostat.

7.5.4 Pneumococcal-13 conjugate vaccine administration (standard of care)

As a standard of care, pneumococcal-13 conjugate vaccine (Prevnar-13™) will be administered to many of autologous HCT recipients at around day +90 (prior to the initiation of maintenance therapy).

7.6 Treatment compliance

Records of study medication used, dosages administered, and intervals between visits will be recorded during the study. Drug accountability will be noted and patients will be asked to return all unused study medication.

8 Visit schedule and assessments

8.1 Visit schedule

Table 8-1 Evaluation and visit schedule

	Pre-HCT (Screening, not required)	Prior to maintenance (Enrollment: +45 to +180) [§]	Cycle #1 (start between +90 and +180)	Cycle #2****	Cycle #3****	Cycle #4****	Cycle #5****	Cycle #6****	Cycle #7****	Cycle #8****	Cycle #9****	Cycle #10*** *	Cycle #11*** *	Cycle #12*** *	End of study visit (4 weeks (± 14 days) follow up after the first dose of cycle #12)
Consent	X ⁺	X													
Enrollment		X													
H&P (SOC)		X	X ^{SS§}	X	X	X	X	X	X	X	X	X	X	X	X
Concomitant medications		X													
Toxicity (adverse event (AE)) assessment ^{SS}			X	X	X	X	X	X	X	X	X	X	X	X	X
Vital signs (SOC)		X ⁺⁺	X	X	X	X	X	X	X	X	X	X	X	X	X
EKG		X	X [*]	X ^{**}	X ^{**}	X ^{**}									
CBC and CMP (SOC)		X	X ^{***}	X ^{***}	X	X	X	X	X	X	X	X	X	X	X
PT/INR/PTT		X			X			X							X
LDH, cholesterol panel, GGT, uric acid		X													
Urinalysis		X													X
TSH, free T4		X													X
Serum pregnancy test ⁺⁺⁺		X	X	X	X	X	X	X	X	X	X	X	X	X	
SPEP, UPEP and serum free		X			X			X			X			X	

Confidential

light chains (SOC)															
Pneumococcal-13 conjugate vaccine (at around day +90 – SOC)		X [#]													
Peripheral blood research samples	X	X	X ^{****}	X	X			X			X				X
Bone marrow research samples	X [@]	X													X
Stem cell graft research samples	X														

*Single 12 lead EKG will be performed for pre-dose and 3 hours (± 15 minutes) post-dose on days 1 and 5 of cycle 1. A total of 4 EKGs during cycle 1 will be performed.
 **Single 12 lead EKG will be performed for pre-dose on day 1 of cycle 2 and beyond at each cycle (at least through cycle 4). If no significant QTcF prolongation is noted during the first cycle, then QTc monitoring is no longer required beyond cycle 4 (and may be performed at the investigator’s discretion). One EKG per cycle from cycle 2 to 4 (minimum).
 ***CBC to be performed weekly during cycle #1 and #2. CBC/CMP will also be performed on day 5 of cycle 1.
 ****Window to start cycles #2 to #12 would be ±7 days from the planned first day of each cycle.
 + Screening consent for research samples (bone marrow, peripheral blood and stem cell graft)
 ++ Height will be measured at screening visit prior to starting panobinostat maintenance therapy
 +++ Only for women of child bearing potential
 ++++ Peripheral blood research samples will be also collected on day 5 of cycle 1.

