4.2 Secondary

- To evaluate the complete response rate to panobinostat maintenance therapy after autologous HCT.
- To determine the 2-year PFS and OS of autologous HCT followed by panobinostat maintenance therapy in patients with multiple myeloma.
- **Exploratory secondary objectives:**
 - To evaluate histone acetylation (H3 and/or H4) of peripheral blood mononuclear cells
 - To isolate and identify clonotypic B cell progenitors in multiple myeloma patients from the bone marrow, peripheral blood and stem cell grafts.
 - To evaluate T-cell immune response against known myeloma tumor associated antigens while on panobinostat maintenance.
 - To evaluate humoral immunity against pneumococcal serotypes included in the standard of care heptavalent pneumococcal conjugate vaccine, and to assess cellular immune responses against CRM adjuvant found in the heptavalent pneumococcal conjugate vaccine.
 - To evaluate minimal residual disease (MRD) after autologous HCT followed by panobinostat maintenance therapy using flow cytometry
 - To evaluate MRD after autologous HCT followed by panobinostat maintenance therapy using multiplex PCR for CDR3 sequences

5 Overall study design

This is an open-label trial to determine the safety and tolerability of 2 different dosing schedules of single agent panobinostat maintenance therapy in patients with multiple myeloma who underwent high-dose melphalan followed by autologous HCT in patients with multiple myeloma. It is unknown whether the toxicity profile of panobinostat will be accentuated in patients after autologous HCT in the setting of maintenance therapy, hence the dose chosen for maintenance therapy is lower than MTD dosing or other phase 2 studies. There are 2 dosing schedules evaluated in this protocol in order to assess optimal tolerable schedule for panobinostat maintenance therapy after autologous HCT. As secondary

objectives, we will evaluate response after completion of treatment, and 2-year PFS and OS. As correlative studies, we plan to evaluate MRD, and to assess clonotypic B cells following an autologous HCT. We also plan to evaluate T effector immune response after autologous HCT while on panobinostat maintenance therapy.

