8.2 Efficacy assessments

All subjects will be evaluated every 3 months with multiple myeloma restaging (standard of care) including serum protein electrophoresis (SPEP), urine protein electrophoresis (UPEP) and serum free light chains. Response assessment will be performed approximately at cycle 3, 6, 9, and 12 of maintenance panobinostat therapy. Responses will be classified by according to the IMWG response criteria (Appendix C).

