12.1 Data collection and monitoring

Investigators must enter the information required by the protocol onto Case Report Forms (CRFs) for unexpected grades ≥ 3 adverse events and serious adverse events. Additional data to be captured may be identified at the time of study activation or review by ongoing monitoring committees.

13 Statistical methods

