13.1.4 Secondary objective and hypothesis

The secondary objectives of the study are to evaluate following parameters in patients who receive panobinostat maintenance therapy after autologous HCT: overall response rate, best response rate, 2-year PFS and 2-year OS. The exploratory secondary objectives include evaluation of minimal residual disease, frequency of B cell precursors and immune subsets, protein acetylation, and immune response against pneumococcal vaccines and CRM. The association of minimal residual disease, B cell precursors, and immune response with response, PFS and OS will be evaluated using the Cox proportional hazards regression model.

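### 2-year PFS and OS are secondary endpoints, but scheduled visits end nominally 7 to 13 months before month 24 and no text commits to recording either outcome after that

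*Combined protocol and SAP*

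**What the plan says.** Section 4.2 sets the objective "To determine the 2-year PFS and OS of autologous HCT followed by panobinostat maintenance therapy in patients with multiple myeloma". Section 13.1.4 lists "overall response rate, best response rate, 2-year PFS and 2-year OS" among the secondary parameters. Section 13.1 states "The OS and PFS will be estimated using the Kaplan-Meier method", with Greenwood intervals, and "All 30 patients are eligible for secondary endpoints". No section defines time zero, events or censoring for PFS or OS.

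The last column of Table 8-1 (section 8.1) is headed "End of study visit (4 weeks (± 14 days) follow up after the first dose of cycle #12". A footnote adds "Window to start cycles #2 to #12 would be ±7 days from the planned first day of each cycle". The electrophoresis and free-light-chain row is last marked at cycle 12 and has no mark in the end-of-study column.

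Section 8.2 says "All subjects will be evaluated every 3 months with multiple myeloma restaging (standard of care" and gives no end date; its next sentence places response assessment at about cycles 3, 6, 9 and 12. Section 8.3 runs the cycle visits through maintenance until progression or unacceptable toxicity.

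After the last dose, section 7.4.5 requires at least 4 weeks of follow-up for adverse events, and section 10.1.2 covers serious-event reporting to at least 30 days. Section 7.4.4 records the reason for stopping, with progression and death among the listed reasons. Section 12.1 has investigators enter data "onto Case Report Forms (CRFs) for unexpected grades ≥ 3 adverse events and serious adverse events" and leaves further items to be identified later.

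**The concern.** A Kaplan-Meier estimate at 24 months needs patients observed to 24 months. If observation ends with the scheduled visits, the curve stops well before that point. PFS at month 24 would then rest on whichever restaging results exist after the end-of-study visit. OS would rest on survival information that no section plans to gather once a patient is off treatment. If later records exist mainly for patients who stay in care at the centre, censoring may not be independent of outcome.

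Patients who stop early are a second gap. Sections 7.4.5 (long dose delay, with a discretionary exception) and 7.5 (need for another anticancer agent) take the patient off the study. For the same QTcF rule, section 8.3.6 says off study and section 7.4.3 says off study treatment. Section 7.4.4 separates treatment from observations without saying which observations continue. Yet section 13.1 counts all 30 patients for these endpoints.

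Third, the time origin is open. The wording of section 4.2 leans towards transplant (HCT), but sections 13.1 and 13.1.4 do not settle it, and the same data give different 2-year figures under the two choices.

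**Working it through.** **Conventions.** One month = 30.4375 days, so 24 months = 730.5 days.

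**The plan's own figure.** Section 3 gives 12 cycles x 4 weeks = 48 weeks. In days, 12 x 28 = 336, which matches.

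**Last scheduled visit from first dose.** Cycle 12 day 1 is 11 x 28 = day 308, and the last visit is 308 + 28 = day 336 (11.0 months). With the ±7-day window at cycle 12 and the ±14-day visit window, the range is 301 + 14 = 315 to 315 + 42 = 357.

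**Last scheduled visit from HCT, and the gap to month 24.** Sections 3 and 7.1 and Table 8-1 start maintenance at +90 to +180. Inclusion criterion 5 (section 6.1.3) allows a start from +45, so these passages need reconciling.

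| Origin and start | Last visit (day) | Gap to month 24 |
|---|---|---|
| First dose | 336 | (730.5 - 336)/30.4375 = 13.0 months |
| HCT, start +45 | 45 + 336 = 381 | 11.5 months |
| HCT, start +90 | 90 + 336 = 426 | 10.0 months |
| HCT, start +180 | 180 + 336 = 516 | 7.0 months |

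**Latest case before dose delays.** If every cycle window is used late and the delays accumulate, the visit falls at 308 + 11 x 7 + 42 = day 427 from first dose. For a start at +180 that is 180 + 427 = day 607 from HCT (19.9 months), still 4.1 months short.

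**Dose delays.** Eleven delays of 28 days plus the +14-day visit window give 336 + 308 + 14 = day 658 from first dose, still short. From HCT that is day 748 to 838 for starts at +90 to +180, past month 24, but only in this extreme.

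**An early stopper.** If the last dose is near day 20 of cycle 1 (assumption), required adverse-event follow-up ends near day 48 from first dose, or day 138 to 228 from HCT for starts at +90 to +180.

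**Events after the last visit (illustration).** Assume exponential PFS, S(t) = 2^(-t/median), with medians of 23 and 41 months (the two arms of IFM 05-02 in section 1.1.1), n = 30 and no dropout.

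- First-dose origin, median 23: S(336 d) = 0.717 (21.5 patients event-free) and S(24) = 0.485. Events by month 24: 30 x 0.515 = 15.4, of which 30 x (0.717 - 0.485) = 7.0 come after the visit (45%).
- First-dose origin, median 41: S(336 d) = 0.830 (24.9 event-free) and S(24) = 0.666. Events 10.0, of which 4.9 after (49%).
- HCT origin, patients event-free at start t0, so the time left to month 24 is 730.5 - t0. Median 23: t0 = 90 gives 14.1 events, 5.6 after (40%); t0 = 180 gives 12.6, 4.1 after (33%). Median 41: t0 = 90 gives 9.0, 3.9 after (43%); t0 = 180 gives 7.9, 2.8 after (35%).

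**Effect of the origin.** Patients enter event-free at t0, so the HCT-origin 2-year PFS is S(24)/S(t0). With no memory in the exponential, the first-dose figure is S(24). The difference is 4.5 points (t0 = 90) to 9.5 points (t0 = 180) at median 23, and 3.4 to 7.0 points at median 41.

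**What delayed entry changes.** Take median 23 and starts spread evenly over +90 to +180, keeping patients event-free at start. The mean of S(t0) is (23/ln 2) x (0.91474 - 0.83676)/2.957 = 0.875. Without delayed entry the HCT-origin estimate is 0.485/0.875 = 0.554. With delayed entry it is S(24)/S(90 d) = 0.485/0.915 = 0.530. Neither returns to 0.485.

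**The case against.** The strongest reply rests on section 8.2. Its restaging sentence covers all subjects, not only those on treatment, and can fairly be read as open-ended, with the cycle-based assessments on top. That stands in part. Progression data may well exist after the end-of-study visit, but the sentence has no end date, nothing commits to recording the results to month 24, and restaging does not establish survival.

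A reader might infer that progression and death go unrecorded altogether. They do not: section 7.4.4 records either one when it ends treatment, and section 10.1.2 covers fatal serious events. What is missing is follow-up after that point. A reader might also take section 12.1 as proof that PFS and OS will not be collected. That list is plainly not exhaustive, since it also omits doses and response, so its silence proves little.

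The 3.4 to 9.5 points might be read as bias that a delayed-entry analysis would remove. Most of it is conditioning on being event-free at entry, which delayed entry leaves in place. It is only the difference between two definitions of 2-year PFS.

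The practical weight is also limited. These are descriptive endpoints with no hypothesis or assumed rate. Even complete 24-month data on 30 patients give a 95% interval about 0.29 to 0.36 wide for an assumed 2-year rate of 0.8 to 0.5. Finally, section 15.2 makes the consent form part of the protocol. That form was not in the text available, so the absence found here is an absence from that text.

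**Conclusion.** The point holds and should be fixed. As scheduled, the visits cannot deliver two named secondary endpoints: the nominal last visit is 13.0 months short of month 24 from first dose, or 10.0 to 7.0 months short from HCT for starts at +90 to +180 (11.5 months if the +45 start applies). Before dose delays, no patient is at risk at month 24 on scheduled visits alone, under either origin.

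The calendar figures follow from the plan's own text. The shares of events falling after the last visit depend on the exponential form, the borrowed medians and no dropout, and should be read as orders of magnitude.

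The documents do not support a wider conclusion. The completion-rate primary endpoint is untouched, and later restaging could rescue part of the PFS estimate. Survival status after treatment, the end date of restaging, the handling of early stoppers and the time origin remain open.

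**What to change.** Amend Table 8-1 and sections 8.2, 12.1 and 13.1 to:

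- record progression from the existing 3-monthly restaging, and survival status by chart or telephone, to at least 24 months from the chosen origin for every treated patient, including early stoppers;
- list both outcomes as case report form data in section 12.1;
- reconcile the off-study wording in sections 7.4.5, 7.5 and 8.3.6 with the off-study-treatment wording in section 7.4.3, so that early stoppers stay in follow-up for these two outcomes;
- state one time origin with event and censoring rules. First dose is the simpler choice. If HCT is kept, use delayed entry at first dose and report the result as conditional on being event-free at the earliest start;
- reconcile the +45 start in section 6.1.3 with the +90 start in sections 3 and 7.1 and Table 8-1, since the HCT-origin dates depend on it.

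The cost is one amendment. Restaging is already standard of care; the survival check is a small new task, and the consent form should be checked to see that it covers it. The downside is about 7 to 13 more months of passive follow-up before the secondary analysis.
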